12.6 Measuring Instrument

Beverage consumption will be recorded through a beverage journal that will be completed at home by the parents for 3 days (two weekdays and one weekend day). Focus groups will be established to modify this record (Appendix IV) and make it more understandable

and practical for completing to improve the percentage of properly completed and collected journals.

The beverage categories will be based on the 2006 National Health and Nutrition Survey, as follows:

1. Water: bottled water, pitcher, mineral, or tap water;
2. Soft drinks: cola or flavored refreshment;
3. Sugary beverages: juices and nectars, "flavored water" (i.e., water made with powder or syrup), noncarbonated refreshments, and orange juice;
4. Bottled flavored waters;
5. Hot drinks: black coffee, tea, infusions, or cocoa;
6. Drinkable dairy products: milk, drinkable yogurt, milkshakes, atole, whole milk, skim milk, fat-free milk, lactose-free milk, flavored milk, or probiotic beverages;
7. Light drinks: light or zero-calorie soft drinks, zero-calorie flavored drinks, or zero-calorie teas;
8. Bottled teas with calories; and
9. Functional beverages: sports, energy, or isotonic beverages.

13.0 SAMPLE SIZE

Considering the results of the previous study where a mean difference of 80.74 mL was found with regard to water consumption with an SD of 399 mL as well as considering an α of 0.05 and a β of 0.1, we used the following formula to calculate a significant difference in means

$$n = [(Z_{1-\alpha} + Z_{1-\beta})^2 * s^2] / d^2$$
$$[(1.96 + 1.28)^2 * 399^2] / 80.74^2 = 256.36$$

N = 257 children

The sample should include 329 first graders (allowing for a 28% loss margin) who will attend the 2017-2018 school year. This sample represents all of the four intervention schools that participated in the previous study.

2016-2017 school enrollment of the intervention schools participating in the previous study

School	Health Center	First grade	Total	Second grade	Total	Third grade	Total	Total school enrollment
Ramón Durand	Ajusco	32 32	64	31 32	63	26 27	53	341
Xitle	Ajusco	27 29 25	81	28 27 29	84	31 30 29	90	529
Guillén de Lampart	Santa Úrsula	28 26 27	81	31 32 30	93	27 27	54	475
Tlamatini	Santa Úrsula	34 35 34	103	36 37 36	101	33 33 33	99	600
			329		278		243	1,604

	Group I	Xitle	81
	Group II	Guillén de Lampart	81
	Group III	Ramón Durand Tlamatini	167

Based on the school enrollment of the current school year (2016-2017), schools with the same number of first graders will be assigned to Groups I and II. For Group III, the schools with the highest and lowest enrollments will be added.

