Material and methods. A community intervention trial will be conducted at four public elementary schools of the Coyoacán Delegation in Mexico City. It will include healthy first graders during the 2017-2018 school year whose parents agree to participate through verbal informed consent and a signed privacy notice. These parents will complete a baseline 3-day beverage record (two weekdays and one weekend day). The four schools will be assigned to one of three groups: Group I will receive the educational strategy during the first grade; Group II will receive it during first and second grades; and Group III will receive it during the first, second, and third grades. All schools will have water dispensers inside the classrooms, and the children will receive a reusable 600-mL bottle so they are able to consume water on demand throughout the day. A second record of beverage consumption will be obtained by completing multiple interventions within each group, and a third record will be completed 1 year later.

Statistical analyses. Descriptive statistics will be used to summarize the numerical variables with medians, minimums, and maximums. The Kruskal-Wallis test will be applied to compare the baseline intake of beverages among the three groups. In each group, baseline water consumption will be compared with that 1 year after the end of the interventions using the Wilcoxon test.

Ethical Considerations. This research is considered to have minimal risk; thus, the Research Ethics Committee will be asked to approve a request for verbal informed consent, and the parents will be asked to sign a privacy notice. The general health law for research in Mexico will be respected, and ethical clinical practices will be followed. The authors have no conflicts of interest to declare.

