14.0 STUDY VARIABLES

Variable	Operational definition	Variable type	Unit of measurement
Outcome variables			
Percentage of water consumed	Average consumption of water/average consumption of total liquids	Numeric/continuous	%
Total liquid Consumption	Average amount of total liquids consumed per child over a 3-day period	Numeric/continuous	mL
Water consumption	Average amount of water consumed per child over a 3-day period	Numeric/continuous	mL
Effectiveness of educational strategy	Increase in the percentage of water consumed, 1 year after completing the interventions within each group relative to baseline	Qualitative/dichotomous	1: yes 2: no
Secondary variables			
Age	Years old at the beginning of the school year	Numeric/continuous	Years
Gender	The sex indicated on each child's birth certificate	Qualitative/dichotomous	1: male 2: female
BMI	Indicator of the relationship between weight and height	Numeric/continuous	kg/m ²
Health condition	Health condition that (in the opinion of the investigator) enables the participant to have free consumption of water	Qualitative/dichotomous	1: healthy 2: sick
Water consumption per school	Quantity of water consumed in 1 month per participating school	Numeric/continuous	L

Operational Definitions

Educative intervention: Number of times that a student will receive the educational strategy for each elementary school year that they attend

Educational strategy: Set of activities aimed at teaching the importance of hydrating with water and promoting its consumption to maintain one's health (Appendix I)

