15.0 STATISTICAL ANALYSIS

The analysis will be performed using the IBM SPSS version 22.0, and non-parametric statistics will be used.

Baseline measurement of beverage consumption (Time 1). The basal consumption of the different beverage categories will be summarized using medians, minimums, and maximums. We will apply the Kruskal-Wallis test (K of independent samples) to compare the differences in baseline beverage consumption among the three groups.

Baseline measurement and at the end of the interventions (Times 1 and 3). The percentage of water consumed at baseline will be compared with that 1 year after finishing the intervention for each group using the Wilcoxon test.

Comparison among the three groups. The percentage of water consumed will be compared among the three groups 1 year after the intervention is completed using Friedman's test of related samples.

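### The sample size in Section 13.0 has the form of one paired test on all children in mL, so the stated beta of 0.1 was not derived for any planned test, including the primary three-group comparison

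*Combined protocol and SAP*

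**What the plan says.** Section 13.0 takes its inputs from the previous study, where "a mean difference of 80.74 mL was found with regard to water consumption with an SD of 399 mL". It then proceeds by "considering an α of 0.05 and a β of 0.1, we used the following formula to calculate a significant difference in means", and the printed calculation gives 256.36, rounded to 257 children in total. On enrolment it says "The sample should include 329 first graders (allowing for a 28% loss margin", and adds: "This sample represents all of the four intervention schools that participated in the previous study". The allocation table in the same section divides the 329 into 81 (Group I, one school), 81 (Group II, one school) and 167 (Group III, two schools).

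Section 7.1 makes the primary objective a comparison of percentage of water between children given one, two or three interventions. Section 15.0 plans two inferential analyses of that outcome. In the first, the baseline percentage is "compared with that 1 year after finishing the intervention for each group using the Wilcoxon test". In the second, "The percentage of water consumed will be compared among the three groups 1 year after the intervention is completed".

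Two other places use mL or leave the scale open. Section 1.0 describes the paired analysis as "In each group, baseline water consumption will be compared with that 1 year after the end of the interventions using the Wilcoxon test", and Section 14.0 lists water consumption in mL among the outcome variables, defined as "Average amount of water consumed per child over a 3-day period".

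**The concern.** A reader takes beta 0.1 to mean that the trial has a 10% chance of missing the planning difference in its main comparison. The calculation has a different structure from the analysis in three respects:

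- It yields one total N, while the children are then split across three groups.
- It is in mL, while both tests in Section 15.0 are on a percentage.
- It contains no between-group comparison, while the primary objective is one.

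Section 13.0 also does not say whether 80.74 mL is a within-group change or a difference between groups, or whether 399 mL is the SD of a change or of a single measurement. Section 4.5.2 reports only median changes in water from the previous study (167 mL with the intervention, 37 mL without), so 80.74 mL cannot be traced. If the three-group result is not significant, the protocol as it stands gives no valid figure for how likely that was under a real difference.

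**Working it through.** **Inputs.** From Section 13.0: d = 80.74 mL, SD = 399 mL, z-values 1.96 (so two-sided 0.05) and 1.28, groups of 81, 81 and 167, and 28% loss. Applying 28% loss to each group: 81 × 0.72 = 58 and 167 × 0.72 = 120.

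**1. The plan's figure reproduces.** (1.96 + 1.28)² × 399² / 80.74² = 256.36, so 257. This is the one-sample or paired formula. The formula for two independent groups carries a factor 2 and gives 514 per group, so 257 in total is not a between-group size.

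**2. Reading A: 80.74 is a within-group change and 399 its SD.** Power = Φ(d√n / SD − 1.96).

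| n | d√n / SD | Power |
|---|---|---|
| 257 (all children) | 3.244 | 90.0% |
| 237 (all, 28% loss) | 3.115 | 87.6% |
| 81 (Group I or II, no loss) | 1.821 | 44% |
| 58 (Group I or II, 28% loss) | 1.541 | 34% |
| 167 (Group III, no loss) | 2.615 | 74% |
| 120 (Group III, 28% loss) | 2.217 | 60% |

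The 90% holds for all children together. On this reading each group would need 257 to have it.

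**3. Reading B: 80.74 is the largest between-group difference and 399 the SD of the compared values.** Power comes from the noncentral F distribution with λ = Σ n_g(μ_g − μ̄)² / SD². The plan gives no pattern of group means, so three are assumed. An independent-groups test is used because the groups are different children (Section 15.0 names Friedman's test of related samples).

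| Means, Groups I / II / III (mL) | λ at 58/58/120 | Power | λ at 81/81/167 | Power |
|---|---|---|---|---|
| 0 / 40.37 / 80.74 | 1.66 | 19% | 2.31 | 25% |
| 0 / 80.74 / 80.74 | 1.79 | 20% | 2.50 | 27% |
| 0 / 0 / 80.74 | 2.42 | 26% | 3.37 | 35% |

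Readings A and B are alternatives. The same 80.74 mL cannot be both, and the two sets of figures should not be added or quoted together as one result.

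**4. The one within-group change the documents report.** Section 4.5.2 gives a median increase of 167 mL at 8 months. Taking it as a rough mean with change SD 399, at n = 58: 167 × √58 / 399 − 1.96 = 1.23, so power is about 89%.

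**5. Loss allowance.** 257 × 1.28 = 328.96, which is the 329. But 1 − 257/329 = 21.9%, so 329 leaves 257 evaluable only if loss is about 22%. With 28% loss, 329 × 0.72 = 237 remain; keeping 257 would take 257 / 0.72 = 357, more than the schools enrol.

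**The case against.** The paired form and the mL scale are not foreign to the plan. Section 15.0 contains a paired test, Section 1.0 describes it on water consumption, and Section 14.0 lists water in mL as an outcome. That stands, but both sections run the test group by group, so the pooled N still matches neither.

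Section 13.0 never says paired, before-after or pooled. Those labels are inferred from the missing factor 2 and the single N. A reader might conclude that the protocol sized a pooled before-after test; the documents support only that the formula has that form. The inference is not needed for the main point, because on a between-group reading 257 in total does not fit either.

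A reader might also infer that every planned test is badly underpowered. The documents do not support that. At the 167 mL increase in Section 4.5.2, even the smallest groups would have about 89% power within group, under the rough assumptions above. And if 399 mL were a single-time SD with an assumed correlation of 0.7, the change SD would be 399 × √(2 × 0.3) = 309 and Group III with no loss would reach 92% at 80.74 mL. Most importantly, both planned tests are on a percentage, for which the documents give neither an effect nor an SD.

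Enrolment is fixed by the four schools. That is a good reason not to ask for more children, but it does not justify keeping an error rate that belongs to another test. The loss allowance is minor: read as a mark-up, 28% reproduces 329, and the cost to the pooled calculation is 90.0% against 87.6%.

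**Conclusion.** The arithmetic in Section 13.0 is correct, but it answers a question that Section 15.0 does not ask. Beta 0.1 was not derived for the within-group tests or for the three-group comparison, and the primary objective has no sample size justification.

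On the mL scale, at the plan's own inputs, power is 34% (Groups I and II) and 60% (Group III) within groups after 28% loss, or 44% and 74% with none, under Reading A. Under Reading B it is 19–26% for the three-group comparison after loss, or 25–35% with none. Both sets assume independent children and two-sided 0.05; Reading B also rests on the assumed patterns of means. What is established is that power for the planned tests is unstated and that the 90% should not be read across to them. A specific shortfall on the percentage scale is not established.

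This needs correcting before the sample size is relied on, because the only stated error rate does not describe the primary comparison. Whether tests that ignore school would reject too often is a separate issue, to be raised as its own point.

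**What to change.** Restate Section 13.0, with no added enrolment, to say:

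- (a) that 329 is the available first-grade enrolment of the four schools;
- (b) what 80.74 mL and 399 mL are: within or between groups, and single-time or change;
- (c) that the calculation is for a single one-sample or paired comparison of all children in mL, with 90% power at 257 only if 399 mL is the SD of that paired change, and that beta 0.1 is not claimed for the per-group or three-group tests;
- (d) the power or detectable difference for the three-group comparison and for each within-group test, at the actual group sizes and on the percentage scale, taken from the previous study's records. The text should note that those records span 8 months, while Section 12.5 runs from October 2017 to between June 2019 and June 2021 depending on group, so SDs and correlations may not carry over, and that the figures assume independent children;
- (e) that 329 covers about 22% loss, or that 28% loss leaves 237 evaluable (87.6% power for the pooled calculation).

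The cost is protocol wording and one reanalysis of the previous study's records, with no extra children or visits. The downside is that the stated power is likely to become less favourable.

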4.5.1 Pedagogical support of the educational strategy "I Prefer Plain Water"

The educational strategy "I Prefer Plain Water" was designed based on the postulates of three theories of knowledge that have proved useful in behavior modification and the development of life skills, which together lead children to build a permanent foundation to acquire healthy lifestyles.

The first theory is *social cognitive* and exposes individuals to the acquisition of knowledge, rules, skills, habits, and strategies by observing others and socializing and interacting with the environment. Here, the individual modifies his or her behavior by observation and modeling. In turn, the individual influences other members of the social environment.

Albert Bandura, lead proponent of this position, argued that it is necessary to identify the influences that explain why and how a behavior is conducted to modify it. These influences are known as "determinants" or "mediators" of behavior.

This strategy uses five mediators to modify behaviors:

Expected results. The strategy enables students to easily visualize the benefits (expected results) that will be gained by simply increasing water consumption through characters in vignettes, posters, and an exchange of knowledge and experiences within the group.

Behavioral capacity. In each educational session, children set a feasible water-consumption goal, monitor themselves for the prescribed time, and acknowledge their progress. They are recognized for their effort, thereby demonstrating that they can adopt the desired behavior (behavioral change of an increase in water consumption).

Modeling and learning by observation. This strategy's core point is the example of the teacher modeling water consumption at different times. Moreover, children can be peer models for each another.

Self-efficacy. This strategy offers students frequent opportunities to drink water and prove to themselves that they are able to change their habits with regard to the expected behavior. Self-efficacy represents a way for them to evaluate whether they are properly hydrated through observing the color of their urine.

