Reinforcements. At each session, the students' achievements are recognized as they approach or meet the set goal; strategies are shared, and participants are encouraged to continue. Commitments are also made within the social circles where they belong, enabling them to strengthen their behavior in personal (strengthening self-esteem and self-care), group, and family situations.

The second theory is that of *social constructivism* posed by Vygotsky, which takes the idea that people construct their knowledge not only via the subject-object relationship but also via a subject-mediator-object triad (i.e., through social interactions with others and the influence of the culture in which they live). Therefore, the classroom activities are not individual but group activities. In addition, through the tasks that are conducted in each session, family members become involved to affect the culture in which they live to promote healthy environments.

Ausubel's theory of meaningful learning states that to promote permanent modification, it is necessary to appeal to intrinsic motivation and meaningful learning based on close situations and the actual needs and interests of children. Therefore, the strategy seeks to have children identify with one of the characters in vignettes and associate the issues presented to them with their own reality. In addition, songs and games are used to playfully assimilate important concepts that strengthen healthy behaviors.

Following the principles of competency learning, the strategy starts from the knowledge, skills, and attitudes presented in children and seeks to enhance them for use as tools that allow them to face problems related to healthcare more effectively in everyday life. Some of the competencies mentioned in the document "Competences for primary education SEP", which are referenced in activities and games, include the capacity for expression through language, decision making, problem solving, individual responsibility, the development of self-esteem, teamwork, the promotion of a culture of prevention, and healthcare and environmental protection.

The third theory is that of *Multiple Intelligences*. Through his theory, Howard Gardner mentions that the world can be perceived via multiple ways of knowing, processing, representing, and communicating information (e.g., with images, words, numbers, body motion, rhythm, and music) as well as being in tune with oneself, with others, and with nature.

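### The sample size and the per-group Wilcoxon tests treat children as independent although the strategy is delivered by class; any positive class correlation lowers power and raises test error, on top of a shortfall that exists without it

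*Combined protocol and SAP*

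**What the plan says.** Section 13 sets the sample size by "considering an α of 0.05 and a β of 0.1". It takes from the previous study that a "mean difference of 80.74 mL was found with regard to water consumption with an SD of 399 mL". It then says "we used the following formula to calculate a significant difference in means". The formula is (Z + Z)² × s² / d², and the result is "N = 257 children", raised to 329 for a 28% loss. The enrolment table in the same section lists 11 first-grade classes in four schools (2 + 3 + 3 + 3). Group I is one school with 3 classes and 81 children. Group II is one school with 3 classes and 81 children. Group III is two schools with 5 classes and 167 children.

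Section 15 says that the percentage of water consumed at baseline "will be compared with that 1 year after finishing the intervention for each group using the Wilcoxon test". That test, like the Kruskal-Wallis and Friedman tests beside it, works on single children.

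On delivery, Section 4.5.1 says that "the classroom activities are not individual but group activities" and describes the strategy's "core point is the example of the teacher modeling water consumption at different times". Under Section 12.4, the first-grade teachers give the sessions and the water dispensers stand in the classrooms. Section 9.0 makes the school the unit of assignment. No section gives an ICC, a design effect or a class term.

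**The concern.** Children in one class share a teacher, the sessions, a dispenser and each other's example. On the plan's own theory of how the strategy works, their changes should resemble one another. A class of 25 to 35 children then carries less information than the same number of unrelated children. A calculation that ignores this overstates power, and a test that ignores it gives p-values that are too small.

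The use made of the results is what is at stake. Section 3.0 wants to learn how many interventions children need and to inform public health policy. A before-after test that rejects too often can make one, two or three rounds look as if they work when the evidence is weak.

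**Working it through.** **Inputs.** From Section 13: d = 80.74 mL, s = 399 mL, so d/s = 0.2024; Z values 1.96 and 1.28; 257 children; 28% loss; 11 classes. The documents give no ICC for change, so 0.01 to 0.10 is an assumed range. The class counts are for 2016-2017 and stand in for the 2017-2018 cohort.

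**1. The plan's figure.** (1.96 + 1.28)² × 399² / 80.74² = 256.36, so 257. This reproduces. It is the one-sample (paired) form. The printed formula shows Z for 1 − α, but the value 1.96 is two-sided.

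**2. Power with no clustering.** Power = Φ(√n × 0.2024 − 1.96).
- n = 257: 90.0%.
- 329 is 257 × 1.28. A 28% loss from 329 leaves 329 × 0.72 = 237, which gives 87.6%.
- Section 15 has no pooled before-after test. Its Wilcoxon tests run within groups, on 81 × 0.72 ≈ 58, 58 and 167 × 0.72 ≈ 120 children. The same formula gives about 34%, 34% and 60%.

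**3. Pooled power with clustering.** Class size m = 257/11 = 23.4; design effect DE = 1 + 22.4 × ICC; power = Φ(√(257/DE) × 0.2024 − 1.96). These figures assume a test that truly holds 5%.

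| ICC | DE | Effective n | Pooled power |
|---|---|---|---|
| 0 | 1.00 | 257 | 90.0% |
| 0.01 | 1.22 | 210 | 83.5% |
| 0.02 | 1.45 | 178 | 76.9% |
| 0.05 | 2.12 | 121 | 60.6% |
| 0.10 | 3.24 | 79 | 43.8% |

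**4. Error of the child-level Wilcoxon test.** True two-sided error ≈ 2 × [1 − Φ(1.96/√DE)]. Groups I and II have 58.3/3 = 19.4 children per class, so DE = 1 + 18.4 × ICC. Group III has 120.2/5 = 24.0, so DE = 1 + 23.0 × ICC.

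| ICC | Groups I and II | Group III |
|---|---|---|
| 0.01 | 7.2% | 7.7% |
| 0.02 | 9.4% | 10.5% |
| 0.05 | 15.7% | 18.2% |
| 0.10 | 24.5% | 28.1% |

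Simulated signed-rank tests with normal class effects (3 classes of 19; 5 classes of 24; 20,000 runs) gave 5.1% and 4.9% at ICC 0, 9.2% and 9.9% at 0.02, and 15.1% and 17.6% at 0.05.

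**5. What a cluster-aware test can do with three classes.** The usual clustered signed-rank statistic is the sum of the class scores divided by the root of their sum of squares. With k classes it cannot exceed √k. For k = 3 that is 1.73, below 1.96, so Groups I and II could never reach significance. A t-test on 3 − 1 = 2 degrees of freedom, with non-centrality √(58.3/DE) × 0.2024, has power of about 13% at ICC 0.02 and 11% at 0.05. If class variance is pooled over all classes (11 − 3 = 8 degrees of freedom), the same non-centrality gives about 21% and 17%.

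**The case against.** The strongest reply is that no ICC is given, so nothing proves that power is below 90% or error above 5%. The outcome is a parent's record kept at home over three days, one of them at a weekend (Section 12.6), and it is read a year after the last round (Section 12.5). Both could weaken class correlation. This stands in part: the direction depends on a positive ICC, and the size depends on its value.

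Second, the pooled power belongs to no planned test. This stands. A reader might infer that clustering is what breaks the 90%, or that 90% would hold if children were independent. The documents support neither reading: the per-group tests fall far short at ICC 0, and Section 13 works in mL while the primary outcome in Sections 7.1 and 14 is a percentage.

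Third, a reader might infer that the Wilcoxon p-value decides whether a group's strategy counts as effective. Section 14 defines effectiveness as a yes/no increase from baseline with no significance criterion, and the objective and hypothesis (Sections 7.1 and 8.0) are between groups. The inflated error therefore harms a planned test, but not a stated decision rule.

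Last, class is not among the variables in Section 14, and nothing says that first-grade classes stay together. The Group II school lists three first-grade and two third-grade classes. A first-grade class effect may be the wrong cluster at the last record.

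**Conclusion.** The point holds conditionally. Sections 13 and 15 contain nothing for class, although delivery is by class. For any positive class-level ICC of change, the 90% is not delivered and the per-group Wilcoxon error exceeds 5%. Even an ICC of 0.01 takes pooled power to about 84% and error to about 7% to 8%. At 0.02 and 0.05, pooled power is about 77% and 61%, and error is about 9% to 10.5% and 15% to 18%.

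The missing term is certain. Its effect is a range under assumed ICCs and 2016-2017 class counts. It adds to the unclustered shortfall of 87.6% pooled and about 34%, 34% and 60% by group. A class correction is also a minimum: with one school each in Groups I and II, school effects cannot be separated from group.

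**What to change.** 1. **Section 13.** Withdraw the 90% statement. Saying that it holds under independence would also be wrong for the planned tests. Restate power for each planned test, per group, on the percentage outcome, with the expected analysed numbers and a design effect of 1 + (m − 1) × ICC. Take the ICC from the previous eight-school study (Section 4.5.2), noting its shorter follow-up, or show a range. Do not add children.

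2. **Section 15.** Record each child's class in each grade. Estimate within-group change from one model across all classes, with group terms, a random class effect with pooled variance, and small-sample degrees of freedom. Do not use separate three-class tests or a clustered signed-rank test. Report estimates with intervals, and keep the child-level Wilcoxon as descriptive only.

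3. **Limits.** State that Groups I and II are one school and three classes each, that the class term is a minimum correction, and that it cannot separate school from group in the between-group comparison.

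**Cost.** Revised wording, one added data item and one model. The price is much wider intervals and a low stated power for within-group claims.

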4.5.2 Effectiveness of the educational strategy “I Prefer Plain Water”

A previous study evaluated the effectiveness of the educational strategy to increase water consumption of first, second, and third graders in Mexico City. For this purpose, a community intervention test was conducted across eight elementary schools in the Coyoacán Delegation during the 2014-2015 school year. A 3-day beverage consumption record (two weekdays and one weekend day) was obtained from all participants. All schools were provided with water bottles inside the classrooms, and the children received a reusable 600-mL bottle. The schools were randomly assigned to an educational intervention group (IG) or a control group (CG). The IG had the educational strategy applied. At the end of the educational session cycle 4 months after baseline, a second record of beverage consumption was obtained, and a third was obtained at the end of the school year (4 months after the second). The strategy was considered effective if the students increased their water consumption by more than 220 mL.

For the analysis, 777 of the 1,105 children included were considered: 413/986 in the IG and 364/762 in the CG with a median age of 7.1 years (range 5.6 to 9.4 years). The children for whom the record of drinks was obtained at all three times were analyzed. From the baseline record to the end (8 months), the IG median increase in water consumption was 167 mL ($P < 0.001$) compared with the CG, which increased 37 mL. The educational strategy was effective for 166/413 of the children in the IG compared with 95/364 of the children in the CG ($P < 0.001$). The IG showed an 80 mL increase in their median total liquid consumption from baseline to first record and a 41 mL increase from the baseline record to the final record. In comparison, the CG increased 33 and 38 mL, respectively. These changes were not significant between the two groups but were significant within the IG from baseline to the first record. Significant differences were found with regard to the consumption of sugary beverages between groups ($P = 0.027$). The IG decreased 42 mL (16.8%), and the CG decreased 36 mL (14.6%) from baseline to the final record. Regarding the consumption of soft drinks, the IG decreased the consumption from 41 mL to 0 mL, whereas the CG reduced from 83 to 33 mL from baseline to the final record ($P < 0.001$). Figure 1 shows the change in beverage consumption in the groups at all three times.

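### The planned 329 children cover a 21.9% loss, not the stated 28%: a 28% loss leaves about 237 instead of the required 257

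*Combined protocol and SAP*

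**What the plan says.** Section 13.0 takes its inputs from the previous study, "a mean difference of 80.74 mL was found with regard to water consumption with an SD of 399 mL", with error rates given as "considering an α of 0.05 and a β of 0.1". The arithmetic is printed as "1.96 + 1.28)^2 * 399^2] / 80.74^2 = 256.36", leading to "N = 257 children".

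The next sentence moves from the evaluable number to the planned number: "The sample should include 329 first graders (allowing for a 28% loss margin"). It is followed by "This sample represents all of the four intervention schools that participated in the previous study". The table beneath gives 2016-2017 first-grade enrolments of 64, 81, 81 and 103 for those schools.

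On loss in the previous study, Section 4.5.2 reports that "777 of the 1,105 children included were considered". Those analysed had beverage records at all three times, and the last record came 8 months after baseline.

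**The concern.** A loss allowance is normally read as a promise: if that fraction of the enrolled children is lost, the required number remains. Here 28% was added to 257, which is a different operation from dividing 257 by 0.72. The section therefore appears to guarantee an evaluable number and a power that it does not deliver at its own loss rate.

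Two further features leave little room for error. The 329 equals the whole prior-year first-grade enrolment, so it is counted before consent, health screening (Section 11.1) and the requirement for a baseline record (Section 11.2). Children with poor session attendance or inadequate records are later removed under Section 11.3. The 28% is also no higher than the loss already seen over 8 months, while Section 12.5 places the final record in June 2019, June 2020 or June 2021 according to group. Those dates are 20, 32 and 44 months after the October 2017 baseline.

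**Working it through.** **Inputs.** Difference d = 80.74 mL, SD s = 399 mL, z-values 1.96 and 1.28, required N = 257, allowance 28%, planned N = 329 (all Section 13.0). Prior retention 777/1,105 (Section 4.5.2).

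**Step 1: reproduce the plan's 257.** n = (1.96 + 1.28)² × 399² / 80.74² = 256.36, rounded up to 257. This reproduces. The formula labels the first term Z(1−α), but 1.96 is the two-sided 5% value, so the calculation is two-sided in effect.

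**Step 2: reproduce the plan's 329.**
- Adding 28%: 257 × 1.28 = 328.96, i.e. 329. This matches.
- Allowing for a 28% loss: 257 / (1 − 0.28) = 356.94, i.e. 357. This does not match; it is 28 more than planned.
- Enrolment: 64 + 81 + 81 + 103 = 329. This also matches.

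**Step 3: what 329 tolerates.** The surplus is 329 − 257 = 72 children. As a share of 257 it is 28.0%; as a share of 329, the number exposed to loss, it is 72/329 = 21.9%.

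**Step 4: evaluable numbers.**
- 28% loss: 329 × 0.72 = 236.9, about 237, which is 257 − 237 = 20 short.
- Loss as in the previous study: 1 − 777/1,105 = 29.7%; 329 × 777/1,105 = 231.3, about 231, which is 26 short. Keeping 257 at that loss would need 257 × 1,105/777 = 365.5, i.e. 366.

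**Step 5: power and detectable difference on the plan's formula.** Power = Φ(√n × 80.74/399 − 1.96). The difference detectable at 90% power is (1.96 + 1.28) × 399 / √n.

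| Evaluable n | Basis | Power | Detectable at 90% power |
|---|---|---|---|
| 257 | plan's requirement | 90.0% | about 81 mL |
| 237 | 28% loss from 329 | 87.6% | about 84 mL |
| 231 | 29.7% loss from 329 | 86.8% | about 85 mL |

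The inflation step alone costs 90.0 − 87.6 = 2.4 points. Moving from 28% to 29.7% costs a further 0.8 points.

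**The case against.** **The margin may be meant as an add-on.** Read as 28% on top of 257, the figure 329 is arithmetically exact. This explains where the number came from, but it does not make 329 cover a 28% loss. The tolerated loss is still 21.9%, and the section does not say so.

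**The effect is small.** This stands. A fall from 90.0% to 87.6% is modest, and no decision in the plan turns on it.

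**The previous study's loss may not carry over.** It counted only children with all three records, whereas the within-group test in Section 15.0 uses Times 1 and 3. Section 12.6 also plans to revise the journal so that more records are completed and returned. Longer follow-up pushes the other way. The documents do not settle the expected loss, so 29.7% is a benchmark and not a forecast.

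Some stronger readings are tempting but not supported:

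- *The intervention-group figure of 413/986 is the true retention, so power would be far lower.* The figures in Section 4.5.2 conflict: "777 of the 1,105 children included were considered: 413/986 in the IG and 364/762 in the CG". The two arm denominators sum to 986 + 762 = 1,748, not 1,105. Until this is reconciled, no power figure should rest on them.
- *The 8-month loss would continue at a constant rate to 20, 32 and 44 months.* The document describes incomplete sets of records; nothing in it shows that loss accrues steadily with time.
- *Nothing is left for refusals or ineligible children.* There is a surplus of 72; the point is that it must serve all these purposes at once.
- *Only 329 children exist to recruit.* The table shows 2016-2017 enrolment, while recruitment is from 2017-2018 first graders. The 329 is a proxy.

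**Conclusion.** The point holds in a limited form. The 28% allowance is applied as a multiplication by 1.28, and the resulting 329 protects 257 evaluable children only up to a 21.9% loss. At 28% loss about 237 remain and power on the plan's formula is 87.6%. At the previous study's overall 29.7% loss about 231 remain and power is 86.8%. These numbers assume that all 329 enter the study, so refusals, exclusions and missing baseline records have to be counted within the same loss.

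All the power figures belong to one calculation: a pooled, one-sample comparison of means in mL. The primary outcome is the percentage of water consumed, and Section 15.0 tests it within and among groups that Section 13.0 sizes at 81, 81 and 167. Neither the stated 90% nor the corrected 88% describes those comparisons, and 357 children would not change that. A reader should not infer that repairing the loss allowance validates the sample size for the primary objective.

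**What to change.** Restate the loss paragraph of Section 13.0 so that it says:

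- keeping 257 evaluable children after a 28% loss would require 257/0.72 = 357;
- about 329 first graders are expected, based on 2016-2017 enrolment, which tolerates a total loss of 21.9%, including refusals, ineligibility and missing baseline records;
- at 28% loss about 237 evaluable children are expected (about 88% power, about 84 mL detectable at 90% power);
- at 29.7% loss, as in the previous study overall, about 231 are expected (about 87% power, about 85 mL detectable);
- these figures apply only to the pooled one-sample calculation in mL and not to the planned comparisons within and among the three groups.

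Reconcile the denominators in Section 4.5.2. If the plan then wants to address longer-term loss, it should show a range of stated assumptions and not a single extrapolation.

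The cost is a few sentences and a slightly less favourable power figure. No additional schools or children are needed for the restatement.
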